3) Per investigator decision and patient discussion, with consideration of age, performance status, medical co-morbidities, Gleason score and other disease features (Gleason score 4+3 vs. 3+4). Strong recommendation is made for consideration of combined modality therapy in intermediate risk and certainly "high intermediate" risk disease as defined by Gleason score 4+3 disease, more than 50% positive cores, and/or PSA velocity of more than 2ng/ml in the year preceding tissue diagnosis, given survival benefit of short term ADT per randomized data in intermediate risk disease. CK SBRT monotherapy would typically be appropriate only for low volume GS 3+4 disease with no other adverse features.

ELIGIBILITY CHECKLIST

(Y) Is there histologically proven prostate adenocarcinoma, biopsy within one year of enrollment?

What is the Gleason Score?

(T1b-4) What is the clinical T-stage? (AJCC 7th Edition)

(Y) Is the patient clinical Nx or N0, and Mx or M0?

(0-50) PSA evaluated 90 days prior to radiation therapy or the most recent PSA evaluated prior to ADT, whichever is applicable

(I, H) Does the patient fall into one of these risk groups (AJCC 6th Edition):
- Intermediate: CS T2b-c, Gleason ≤ 6 , PSA ≤ 10 , or CS T1b-T2a, and Gleason 7, PSA ≤ 10 ng/ml, or Gleason ≤ 6 , PSA 11-20 ng/ml
- High: CS T3-4 or Gleason > 7 and PSA ≤ 50

(Y) Is the prostate volume ≤ 100 cc?

(0-1) What is the ECOG performance status?

(N) Has the patient undergone prostatectomy or cryotherapy of the prostate?

(N) Has the patient had radiotherapy to the prostate or lower pelvis?

(N) Is there implanted hardware near the planning target volume that would prohibit appropriate treatment planning or treatment delivery in the investigator's opinion?

(N) Has the patient had chemotherapy for a malignancy in the last 5 years?

(N) Has the patient had an invasive malignancy (other than this prostate cancer, or basal or squamous skin cancers) in the last 5 years?

(n/a, Y) Has the patient's androgen function been ablated during the past 2 months?

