Based on the data provided in the reports summarized above, and adding a PSA DFS degradation factor to the Gamma West series to compensate for their short median follow-up, the average calculated 5 year HDR monotherapy ASTRO-based PSA DFS is 98% for favorable prognosis, 82% for intermediate prognosis and 59% for unfavorable prognosis cases. There are too few Phoenix-based PSA DFS results to project a meaningful Phoenix-based HDR monotherapy PSA DFS efficacy result.

It is anticipated that the case mix in this study will be approximately 75% intermediate, and 25% high risk prognosis cases, leading to a predicted 5 year PSA DFS rate of 85%-90% for intermediate risk patients, and 75%-80% for high risk patients based on HDR brachytherapy boost trial. **Table 2. Toxicity review for HDR-Monotherapy for Prostate Cancer**

HDR Details	Institution	# pts	Median f/u	>= Gd 3 toxicity		
				Total (%)	GI (%)	GU (%)
6-7.25Gy x 6	CA Endocurie ³⁰	117	3.3	3	0	3
9.5Gy x 4	Beaumont ³¹	95	4.2	8	0	8
7.5Gy x 6	Texas Tech ³²	145	5	5 – 8*	1	4 – 7*
6.5Gy x 6	Gamma West (SLC) ³³	328	1.2	1	0	1
6Gy x 8-9	Osaka (Japan) ³⁴	111	2.25	7	1	6
Totals		796	2.4	6	0 -1	5

*3% acute and 4% chronic grade 3 GU toxicity – It is unclear to what degree acute and chronic grade 3 GU toxicity populations overlap in this study.

To confirm our hypothesis that CyberKnife® radiosurgery may be made to resemble a “noninvasive HDR dosimetry delivery system,” in addition to simply creating equivalent dosimetry, it is necessary to show clinical equivalence both in terms of efficacy and toxicity. Due to short median follow-up, the incidence of >= grade 3 late toxicity is likely underestimated. We project that the incidence of late toxicity will increase by approximately 50% when all data reach 5 years maturity, yielding a projected cumulative 5 year HDR monotherapy grade 3 toxicity incidence of 9% (7-8% GU; 1-2% GI). In this study, biochemical disease-free survival (ASTRO and Phoenix definition), freedom from local recurrence, freedom from distant relapse, clinical disease-free survival, disease-specific survival and overall survival will be recorded. The incidence of grade 3 or higher toxicity and the effect of CyberKnife® radiosurgery on bladder, bowel, and sexual function will be followed and monitored using standardized, patient self-administered questionnaires²⁸ and compared with results published in peer-reviewed literature for other prostate cancer therapeutic modalities.²⁹

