4. PRETREATMENT EVALUATION

- 4.1. Complete history and physical exam
- 4.2. DRE findings from urologist or radiation oncologist
- 4.3. Assessment of performance status
- 4.4. Histological evaluation of prostate biopsy with assignment of Gleason score
- 4.5. Evaluation of the pelvic lymph nodes with CT or MRI is optional
- 4.6. Serum PSA. Laboratory evaluation must be done within 90 days prior to treatment
- 4.7. CBC, platelets, serum BUN and creatinine
- 4.8. The prostate volume may be obtained by prior transrectal ultrasound. A CT or MRI-based prostate volume measurement will also be acceptable (specify which modality).
- 4.9. Patient questionnaires (see Appendix VI).
 - 4.9.1. AUA questionnaire
 - 4.9.2. EPIC-26 questionnaire
 - 4.9.3. SHIM questionnaire

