5. PATIENT SELECTION & ELIGIBILITY

- 5.1. Patient must be \geq 18 years of age.

- 5.2. Histologically proven prostate adenocarcinoma
 - 5.2.1. Gleason score 2-10 (reviewed by reference lab)
 - 5.2.2. Biopsy within one year of date of registration
- 5.3. Clinical stage T1b-T4, N0-Nx, M0-Mx (AJCC 7th Edition)
 - 5.3.1. T-stage and N-stage determined by physical exam and available imaging studies (ultrasound, CT, and/or MRI; see section 4.5)
 - 5.3.2. M-stage determined by physical exam, CT or MRI. Bone scan not required unless clinical findings suggest possible osseous metastases.
- 5.4. PSA \leq 50 ng/ml, CBC, platelets, BUN, creatinine prior to treatment
- 5.5. Patients belonging in one of the following risk groups:
 - 5.5.1. Intermediate: CS T2b-c and Gleason \leq 6 and PSA \leq 10, or CS T1b-T2b, and Gleason 7 and PSA \leq 10 ng/ml, or Gleason \leq 6 and PSA 11-20 ng/ml
 - 5.5.2. High: CS T3-4, Gleason score >7 and PSA \leq 50
- 5.6. Prostate volume: \leq 100 cc
 - 5.6.1. Determined using: volume = $\pi/6 \times$ length \times height \times width
 - 5.6.2. Measurement from MRI, CT or ultrasound prior to registration.
- 5.7. ECOG performance status 0-1
- 5.8. No prior prostatectomy or cryotherapy of the prostate
- 5.9. No prior radiotherapy to the prostate or lower pelvis
- 5.10. No implanted hardware or other material that would prohibit appropriate treatment planning or treatment delivery, in the investigator's opinion.
- 5.11. No chemotherapy for a malignancy in the last 5 years.
- 5.12. No history of an invasive malignancy (other than this prostate cancer, or basal or squamous skin cancers) in the last 5 years.
- 5.13. Completion of patient questionnaires in section 4.7.
- 5.14. Consent signed.

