6.2. PATIENT REGISTRATION: Patients may be registered only after all eligibility criteria are met: see Eligibility Checklist above, and Inclusion Criteria and Exclusion Criteria CRFs (Case Report Forms). After the patient signs the Consent Form the patient is enrolled in the study, and scheduled for treatment. The pre-treatment CRFs are then filled out by the investigator and/or research associate. This data is retained in the patient's chart located in the research office. The date of registration may be the date the consent was signed. Fiducials must be placed within 60 days, and the first fraction of radiosurgery must be administered within 90 days of registration.

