8. TREATMENT: CYBERKNIFE® RADIOSURGERY

- 8.1. Intermediate risk patients will be treated with either: CyberKnife® SBRT boost of 21 Gy (7 Gy X 3) followed by prostate/SV IMRT 45-50.4 Gy (treatment planning and delivery per current standards of care); or CyberKnife® SBRT monotherapy 36.35Gy (7.27Gy x 5). Short term Androgen Deprivation Therapy (4-6 months per standards of care) is strongly recommended for all intermediate risk patients.

High risk patients will be treated with CyberKnife® boost of 21 Gy (7 Gy X 3) followed by whole pelvis IMRT 45-50.4 Gy (treatment planning and delivery per current standards of care). Short or long term ADT (6 months up to 3 years per current standards of care) is strongly recommended for high risk patients.

Standards of care are based on National Comprehensive Cancer Network guidelines. Per investigator decision and patient discussion, the appropriate treatment plan will be determined for each patient based on their risk group outlined by these guidelines. Patient age, performance status, medical comorbidities, Gleason score and other disease features (Gleason score 4+3 vs. 3+4) will be taken into consideration. Strong recommendation is made for consideration of combined modality therapy for patients with : Gleason score 4+3 disease, more than 50% positive cores, and/or PSA velocity of more than 2ng/ml in the year preceding tissue diagnosis, given survival benefit of short term ADT. CyberKnife® SBRT monotherapy would typically be appropriate only for low volume GS 3+4 disease with no other adverse features.

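### Baseline EPIC-26 and SHIM may be completed on ADT and results are not split by ADT, so change in sexual and hormonal scores after CyberKnife is confounded, in a direction that depends on ADT timing

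*Combined protocol and SAP*

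**What the plan says.** The eligibility checklist asks whether the patient's "androgen function been ablated during the past 2 months" and lists n/a and Y as acceptable answers; N is not listed. Section 6.2 makes the checklist binding: "Patients may be registered only after all eligibility criteria are met". Section 5 has no matching ADT criterion.

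The checklist allows for ADT begun before entry when it deals with PSA, where it accepts "the most recent PSA evaluated prior to ADT, whichever is applicable". The questionnaires have no such provision. Section 4.9 lists AUA, EPIC-26 and SHIM as pretreatment items ("Patient questionnaires (see Appendix VI"). Section 5.13 makes them an entry condition ("Completion of patient questionnaires in section 4.7"), although 4.7 is the blood tests and the questionnaires are at 4.9. Neither section ties them to the start of ADT.

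On treatment, Section 8.1 states: "Short term Androgen Deprivation Therapy (4-6 months per standards of care) is strongly recommended for all intermediate risk patients". That covers monotherapy and boost alike. For high-risk men it strongly recommends 6 months to 3 years of ADT. No start date is given for either group.

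Section 11.1 reports quality of life descriptively by treatment group: monotherapy, and a boost group whose label includes whole pelvis IMRT and ADT. No analysis by ADT use, timing or duration is planned. The Background says that "the effect of CyberKnife® radiosurgery on bladder, bowel, and sexual function will be followed and monitored" and that results will be compared with published results for other treatments.

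**The concern.** ADT itself can affect sexual function and produce the symptoms in EPIC-26 item 13, such as hot flashes, breast changes and low energy. If some men complete the baseline on ADT and others do not, and follow-up visits fall variously during or after ADT, a change score combines the radiation effect with the start or end of hormone treatment. The treatment-group split does not separate the two: monotherapy men may have ADT, boost men may not, and intermediate-risk men given boost with prostate/SV IMRT fit neither label in Section 11.1.

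Sexual function is prominent in the rationale. Section 1.13 proposes better preservation of potency than with HDR brachytherapy, and Section 12.3 lists lower sexual toxicity than other radiation or prostatectomy as a possible benefit. A comparison with published series would carry the ADT effect with it, unlabelled.

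**Working it through.** The plan gives no figure on this point. Its only calculated figures are the sample sizes of 32 (5-year PSA DFS of 80%) and 40 (70%). Both reproduce as the smallest n giving an exact (Clopper-Pearson) 95% interval no wider than 0.30: the widths are 0.2985 at n = 32 and 0.2997 at n = 40. They do not concern quality of life and are unaffected.

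**Recall periods (Appendix VI).** The EPIC-26 sexual and hormonal items ask about the last 4 weeks, so they can fall wholly within a period of ablation that began up to 2 months earlier. SHIM asks about the past 6 months. If ablation began within the past 2 months, at least 6 − 2 = 4 of those months precede ADT. EPIC-26 is therefore the more exposed instrument.

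**ADT against the visits.** Questionnaires fall at months 1, 3, 6, 12, 18, 24, 30, 36, 48 and 60 from the last radiation treatment, each within 30 days (Section 9 table and 9.1.3). On the first fraction, Section 6.2 says "the first fraction of radiosurgery must be administered within 90 days of registration".

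- *ADT begun by registration, 4-6 months.* It ends no later than 6 months after registration. Radiation ends after registration, so ADT is over by about the month-6 visit and at all seven visits from month 12 to month 60. An on-ADT baseline is then compared with off-ADT follow-up.
- *ADT begun at registration, 3 years.* With up to 3 months to the first fraction and a visit up to 1 month late, the month-24 visit falls at most 3 + 24 + 1 = 28 months after registration, plus the length of the radiation course. That is well inside 36 months, so the visits to month 24 fall during ADT. Months 48 and 60 fall after it.
- *ADT begun after baseline, at the start of monotherapy, 4-6 months.* The baseline is free of ADT, and the month-1 and month-3 visits are on it.

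**Direction and size.** Let c be the true loss due to CyberKnife, a0 the points by which ADT lowers the score at baseline, and a1 the same at the visit.

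Observed loss in an ADT man = c + (a1 − a0)

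Error in the pooled loss = (share of men with ADT) × (a1 − a0)

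The documents give no score, SD, ADT effect or ADT share. The figures below are assumptions for illustration: a 0-100 domain, an ADT effect of at most 20 points, and the same a0 and a1 in every ADT man. Negative means that loss is understated.

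| a0 | a1 | Situation | Share 25% | 50% | 75% | 100% |
|---|---|---|---|---|---|---|
| 20 | 0 | full effect at baseline, gone at visit | −5 | −10 | −15 | −20 |
| 20 | 10 | partly recovered at visit | −2.5 | −5 | −7.5 | −10 |
| 20 | 20 | equal at both | 0 | 0 | 0 | 0 |
| 10 | 20 | still developing at baseline | +2.5 | +5 | +7.5 | +10 |
| 0 | 20 | ADT starts after baseline | +5 | +10 | +15 | +20 |

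The sign changes with timing, which the plan does not fix.

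**The case against.** The strongest objection is to a reading that the checklist invites: every man on ADT is registered after ablation, so baselines are lowered and loss after CyberKnife is understated. The documents do not support this, for three reasons.

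- It rests on one ambiguous checklist line that Section 5 does not repeat. The answer n/a may cover men who start ADT after registration.
- Understatement requires ADT to act at baseline and to have worn off by the visit. With courses of up to 3 years and visits from month 1, many visits can fall during ADT, and loss is then overstated if ADT acts more strongly at the visit than at baseline. A fixed understatement in every ADT man would require the effect to be complete at baseline and fully gone at follow-up.
- A baseline SHIM is only partly an on-ADT score, given its 6-month recall.

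These objections stand against a fixed direction. They do not remove the confounding: overstatement at early visits and understatement at late ones have the same cause, and neither can be seen in tables by treatment group.

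It can also be said that Section 11.1 plans description only, with no change-from-baseline estimand, and that the case report forms (Appendix IV), which are not shown, may already collect ADT dates. The first limits the weight of the point, but the Background still speaks of the effect of CyberKnife on sexual function. The second could make the fix cheaper; it does not supply the missing analysis.

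Finally, men with no ADT may be few and selected, because ADT is strongly recommended for both risk groups. That is a true limit on the remedy.

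**Conclusion.** The concern holds in a limited form. Men may complete baseline EPIC-26 and SHIM after ADT has begun, ADT use is likely to be mixed within treatment groups, and no split by ADT is planned. As written, the plan cannot separate the effect of CyberKnife on sexual and hormonal scores from that of ADT.

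Understatement is plausible at late visits for men on ADT at baseline who have since stopped, assuming some recovery after stopping. Overstatement is plausible at visits during ADT and when ADT starts around or after baseline. No overall direction can be claimed, and the size cannot be derived from the documents. The range of −20 to +20 points in the table follows entirely from the assumed 20-point effect.

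The importance is minor: a secondary, descriptive objective is affected.

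**What to change.** In Section 11.1, report the EPIC-26 sexual and hormonal domains and SHIM, both level and change, separately for men who never received ADT and men who received any ADT. Record ADT start and stop dates, and use them to label each questionnaire, including baseline, as completed before, during or after ADT. The strata should rest on any ADT exposure: a split on ADT status at baseline alone would place later starters in the group without ADT.

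Base statements about CyberKnife's effect on sexual function on the no-ADT men, and say that they are a smaller, selected group. State also that the split does not restore a pre-ADT baseline for men who entered on ADT. Correct the cross-reference in Section 5.13 to 4.9.

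The cost is two date fields, if the case report forms do not already hold them, one further split of descriptive tables, and smaller subgroups. No change to treatment or sample size is needed.

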1. BACKGROUND

- 1.1. During the prostate-specific antigen era, an ever-increasing percentage of men with prostatic adenocarcinoma have presented with clinically localized, potentially curable disease. Conventional treatment options for these patients include laparoscopic or open radical prostatectomy, external beam radiation therapy, permanent source interstitial brachytherapy, and high dose rate (HDR) remote after loading brachytherapy, either as monotherapy, or in combination with external beam radiotherapy.¹
- 1.2. Although each of the treatment options is potentially curative in selected patients, each treatment option also has drawbacks. The post-operative recovery period may be substantial following radical prostatectomy; the period of urologic symptoms may be protracted and occasionally severe following permanent source brachytherapy; the scheduling duration is substantial for external beam radiotherapy and the discomfort of indwelling transperineal catheters is significant for HDR brachytherapy patients. Additionally, all local treatments carry a risk of negative long-term quality of life consequences, and occasionally, serious complications.
- 1.3. The use of hypofractionated CyberKnife® stereotactic therapeutic radiation as a modality of treatment for early-stage prostate cancer has also been described.^{2,3,4} In contradistinction to traditional external beam radiotherapy, this method entails a therapeutic radiation process that uses a more precise targeting methodology, allowing a more focal treatment margin around the prostate. This more effectively limits the volume of adjacent tissue receiving high dose radiation, which in turn allows the delivery of a much shorter series of treatments, employing a much larger dose of radiation per treatment. When so applied, the radiation becomes tissue ablative within the high dose zone, and as such, may be described as a form of radiosurgery.
- 1.4. Although limited experience has been gained to date, the radiosurgical approach for prostate cancer carries with it a number of potential advantages, including the possibility of lower morbidity due to the very small treatment margins, more rapid recovery from side effects due to the lack of a surgical resection or implanted radioactivity, convenience of a one week treatment course, and lack of transperineal HDR catheters with their attendant pain and hospital admission requirement.
- 1.5. The main technical problem that prevents the application of radiosurgery for prostate cancer is that the prostate may move substantially, both between fractions (interfraction motion) and during the treatment itself (intrafraction motion), even if rigid body immobilization is applied, due to the effect of organ motion.^{5,6} This prostate motion effect necessarily leads to the application of a larger radiotherapy planning target volume to compensate, effectively rendering radiosurgery impossible by traditional radiotherapy or radiosurgical systems.
- 1.6. The CyberKnife® is a unique noninvasive radiosurgical system, capable of treating any part of the body from any of approximately 1600 different targeting

angles, creating a highly conformal three-dimensional radiosurgical treatment volume, guided by orthogonal X-ray-based targeting feedback, and delivering radiation by a highly collimated, robotically controlled linear accelerator. The CyberKnife® system targets implanted fiducial markers with sub-millimeter initial set-up accuracy, and continuously updates the planning target volume by obtaining multiple intrafractional orthogonal X-ray-images, producing an automated robotic adjustment after each X-ray feedback step, resulting in a real-time target volume tracking process that maintains millimeter accuracy throughout the radiosurgical treatment.⁷ Thus, the CyberKnife® device allows a reproducible method of radiosurgical prostate treatment.

- 1.7. There are also radiobiological data that suggest hypofractionated radiosurgical treatment may be advantageous for prostate cancer, as contemporary data suggest the α/β ratio for prostate cancer tissue may be as low as 1.5Gy.⁸ These values of α/β are comparable to, if not lower, than late-responding normal tissues.⁸ This means that in addition to causing effective cancer cellular ablation and tissue sparing due to of its physics attributes, a course of hypofractionated CyberKnife® prostate radiosurgery may also create a favorable therapeutic ratio by virtue of the radiobiologic sensitivity of prostate cancer itself to hypofractionation, effectively resulting in radiobiologic tumor dose escalation.^{8,9}
- 1.8. From a dosimetry standpoint, CyberKnife® radiosurgery appears capable of producing a dose distribution comparable to that created by prostate HDR brachytherapy treatment, without the invasive transperineal catheters. As such, the CyberKnife® prostate radiosurgery dose fractionation schedule prescribed in this study is based upon prior published prostate HDR brachytherapy experience, which suggests efficacy and safety, with a long follow-up. Hypofractionation with brachytherapy using high-dose-rate (HDR)-brachytherapy has demonstrated excellent efficacy and toxicity profiles as both monotherapy and post-EBRT-boost for localized PCa¹⁰⁻²¹. The University of California San Francisco (UCSF) has recently reported its HDR-brachytherapy-boost experience in mostly intermediate to high risk disease, achieving five-year bNED rates of 93% with minimal toxicity. A randomized phase III trial has reported superior bNED rates with HDR-brachytherapy-boost over EBRT alone, and a recent systematic review of the world literature has concluded that the combination of EBRT and HDR-brachytherapy results in superior bNED and overall survival (OS) as compared to EBRT alone or EBRT plus permanent prostate seed implant (PPI)-boost. Others have also reported equivalent disease control and improved toxicity and quality of life (QOL) measures with HDR brachy-monotherapy as compared to PPI monotherapy.
- 1.9. The radiosurgery volume in this study will be made to resemble prostate HDR brachytherapy therapeutic volume as closely as possible, with similar dose limitation objectives to adjacent tissues, including the rectum, bladder and urethra.

1.10. As most patients with low and intermediate risk prostate cancers survive at least 10 years after intervention, the morbidity associated with therapy for early stage prostate cancer is a crucial factor of patient outcome.

1.11. Although traditional, physician-reported toxicity data are a useful component for evaluating treatment-related morbidity, it has been shown that patient-report data (collected via standardized questionnaires) are more sensitive than physician reports to the full severity and broad range of therapy effects on patient Health-Related Quality of Life (HRQOL), particularly among men with prostate cancer.²⁵

1.12. The feasibility of CyberKnife® for treating localized prostate cancer was first described by King at Stanford University. Their phase I protocol delivered 36.25Gy in 5 fractions of 7.25Gy. In a recent report of acute and 18-month late toxicity in 26 “low-risk” patients, no patient experienced grade 3 or 4 acute or late toxicity, and only one patient experienced a grade 2 late morbidity (urethral stricture). Toxicity was less than that reported in MD Anderson’s external beam dose escalation trial. Mean PSA 18 months after treatment was 0.22ng/m²⁵. Similar excellent results have also been reported by Jabbari et al. from the University of California for both CyberKnife® monotherapy and boost post whole pelvic radiation therapy³, and King and Freedman using the original Stanford fractionation of five fractions when used as monotherapy⁴.

1.13. Another potential benefit of CyberKnife® radiosurgery relative to HDR brachytherapy is better preservation of potency, even if the radiation distribution is essentially identical between these modalities. This is so because needle trauma has been identified as a potentially significant contributory factor to erectile dysfunction with brachytherapy, including HDR-based monotherapy technique, presumably due to direct physical injury to the neurovascular bundle and/or bulb of the penis, particularly when greater than 13 needle insertions are performed.²⁷ By comparison, CyberKnife® radiosurgery is noninvasive, and so removes this particular erectile dysfunction risk factor.

Table 1. 5-Year bDFS Outcomes for HDR-Monotherapy for Prostate Cancer

HDR Details	Institution	#pts	Median f/u yrs	Phoenix	ASTRO
6–7.25 Gy x 6	CA Endocurie ³⁰	117	3.3		97%
9.5 Gy x 4	Beaumont ³¹	95	4.2		98%
7.5 Gy x 6	Texas Tech ³²	145	5		90%
6.5 Gy x 6	Gamma West – Fav. (SLC) ³³	209	1.2	96%*	99%*
	Gamma West – Int. ³³	119	1.2	89%*	89%*
6 Gy x 8-9	Osaka (Japan) ³⁴	111	2.25		70%†
Totals		796	2.4		90%

*3 year result; Projecting constant failure rate in this series to 5 years yields 98% and 82% ASTRO-definition PSA DFS for favorable and intermediate risk cases, respectively. †Predominantly unfavorable prognosis cases in this series; 5 year local control is 97%.

Based on the data provided in the reports summarized above, and adding a PSA DFS degradation factor to the Gamma West series to compensate for their short median follow-up, the average calculated 5 year HDR monotherapy ASTRO-based PSA DFS is 98% for favorable prognosis, 82% for intermediate prognosis and 59% for unfavorable prognosis cases. There are too few Phoenix-based PSA DFS results to project a meaningful Phoenix-based HDR monotherapy PSA DFS efficacy result.

It is anticipated that the case mix in this study will be approximately 75% intermediate, and 25% high risk prognosis cases, leading to a predicted 5 year PSA DFS rate of 85%-90% for intermediate risk patients, and 75%-80% for high risk patients based on HDR brachytherapy boost trial. **Table 2. Toxicity review for HDR-Monotherapy for Prostate Cancer**

HDR Details	Institution	# pts	Median f/u	>= Gd 3 toxicity		
				Total (%)	GI (%)	GU (%)
6-7.25Gy x 6	CA Endocurie ³⁰	117	3.3	3	0	3
9.5Gy x 4	Beaumont ³¹	95	4.2	8	0	8
7.5Gy x 6	Texas Tech ³²	145	5	5 – 8*	1	4 – 7*
6.5Gy x 6	Gamma West (SLC) ³³	328	1.2	1	0	1
6Gy x 8-9	Osaka (Japan) ³⁴	111	2.25	7	1	6
Totals		796	2.4	6	0 -1	5

*3% acute and 4% chronic grade 3 GU toxicity – It is unclear to what degree acute and chronic grade 3 GU toxicity populations overlap in this study.

To confirm our hypothesis that CyberKnife® radiosurgery may be made to resemble a “noninvasive HDR dosimetry delivery system,” in addition to simply creating equivalent dosimetry, it is necessary to show clinical equivalence both in terms of efficacy and toxicity. Due to short median follow-up, the incidence of >= grade 3 late toxicity is likely underestimated. We project that the incidence of late toxicity will increase by approximately 50% when all data reach 5 years maturity, yielding a projected cumulative 5 year HDR monotherapy grade 3 toxicity incidence of 9% (7-8% GU; 1-2% GI). In this study, biochemical disease-free survival (ASTRO and Phoenix definition), freedom from local recurrence, freedom from distant relapse, clinical disease-free survival, disease-specific survival and overall survival will be recorded. The incidence of grade 3 or higher toxicity and the effect of CyberKnife® radiosurgery on bladder, bowel, and sexual function will be followed and monitored using standardized, patient self-administered questionnaires²⁸ and compared with results published in peer-reviewed literature for other prostate cancer therapeutic modalities.²⁹

